Empirical evidence consistently demonstrates that caregivers of children with cancer experience significantly higher levels of psychological distress compared to the general population. Elevated rates of anxiety, depression, and post-traumatic stress symptoms have been widely reported (Bashir et al., 2024). In similar contexts, up to 87.8% of caregivers exhibit symptoms of anxiety, while 45.9% experience depression (Wang et al., 2025). In Pakistan, recent findings

indicate that approximately 52.94% of caregivers of pediatric cancer patients report high levels of post-traumatic stress symptoms, with female caregivers and those with lower educational attainment being particularly vulnerable(Bashir et al., 2025). These psychological challenges can undermine caregivers' coping capacity, reduce their ability to effectively support treatment adherence, and ultimately impact the child's health outcomes and quality of life(Kumari et al., 2018). Moreover, evidence suggests a reciprocal relationship between caregiver and child adjustment, highlighting the importance of addressing caregiver well-being as part of comprehensive pediatric oncology care.

Caregiver adaptation to a child's illness is not a static outcome but a dynamic process that evolves across different phases of the disease over time(Ververidou et al., 2023). The initial diagnosis phase is often characterized by shock, disbelief, and acute emotional distress(Mess et al., 2022). During the intensive treatment phase, caregivers must continuously adjust to demanding treatment regimens, frequent hospital visits, and uncertainty regarding outcomes(Rachmad, 2022),that enable individuals to function effectively and to ease distress.(Avsec et al., 2022). The maintenance or survivorship phase introduces additional challenges, including fear of relapse, management of long-term treatment effects, and reintegration into daily life(Perkins, 2022). Each phase imposes unique adaptive requirements, necessitating different coping strategies and supportive interventions.

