Nature of associations between the intervention components.	The intervention includes family needs assessment, stage-matched psychoeducation (based on the family's adaptation phase), dyadic communication support, problem-solving skills training, and linkage to social and spiritual resources. These components are delivered in a sequence that follows the family's evolving adaptation process rather than a rigid protocol. To minimize bias, assessments at baseline, post-intervention, and follow-up will be conducted by research assistants blinded to group allocation. Trained mental health nurses will deliver the intervention under the supervision of a clinical psychologist to ensure fidelity to the Transactional Family Adaptation Model.
Complexity of actions needed by professionals conducting the intervention.	The intervention requires mental health nurses to assess the family's current adaptation status, including demands (e.g., illness severity, financial strain), capabilities (e.g., coping resources, family cohesion), and appraisal processes (e.g., meaning-making, sense of coherence). Based on this assessment, nurses must select and apply appropriate modules to strengthen family adjustment. The principal researcher will provide rigorous training on the Transactional Family Adaptation Model, cultural nuances of family dynamics in Pakistan. A supervising psychologist will oversee sessions, address any adverse psychological reactions, and ensure that religious and cultural sensitivities are respectfully integrated into the intervention.

The complexity of actions needed by parent caregivers.
	
Parent caregivers must engage in structured sessions that involve reflecting on family strengths, identifying sources of stress, participating in joint problem-solving with their spouse or extended family, and practicing communication skills to coordinate caregiving roles. The intervention accommodates varying literacy levels by using verbal delivery and pictorial aids in Urdu, and sessions are scheduled flexibly around treatment cycles to reduce attrition, recognizing that multiple family members may need to participate.

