
The quantity and range of outcome measures.
	
To capture the multidimensional impact of the intervention, outcomes will include caregiver's adaptation, burden, perceived social support and psychological distress such as depression, anxiety and Stress. Exploratory outcomes will assess caregiver problem-solving capacity and child treatment adherence, where feasible. Unintended outcomes will be qualitatively explored through process evaluation..

The degree to which the intervention permits personalization and how this influences progress and evaluation.
	
The intervention is inherently personalized, as it responds to each caregiver's unique constellation of demands (e.g., illness phase, socioeconomic status, family structure), capabilities (e.g., social support, financial resources, religious coping), and appraisal processes (e.g., how the family makes meaning of the illness). However, to maintain replicability, the intervention is manualized with structured, module-based content that addresses common adaptation challenges. Cultural adaptation is embedded across all modules, incorporating religious coping strategies , collectivist family dynamics, and the hierarchical decision-making structures typical in Pakistani families. This balance between standardization (to ensure fidelity) and flexibility (to meet individual caregiver needs) allows for meaningful evaluation.

Theoretically, it is necessary to comprehend how the intervention leads to change, pinpointing and enhancing any vulnerable links in the cause-and-effect sequence.	Previous research and clinical insights suggest that each component of the intervention is linked to specific transitional effects, ultimately influencing the desired outcomes and ultimately reducing caregiver distress and improving the child's care environment.
----------------------------------------------------------------------------------------------------------------------------------------------------------------------------	------------------------------------------------------------------------------------------------------------------------------------------------------------------------------------------------------------------------------------------------------------------------

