Focus group and Delphi	To elicit comments on the model stage-matched intervention.	Parent caregivers will be engaged in focus groups to give their opinions on the model intervention developed from integrated information from earlier stages. Professionals	Delphi will be e-Delphi, and focus groups will be at participating tertiary care facilities.	As with the first interview, transcription and content analysis of discussions will be done. Expert opinion will be analysed using two indicators: the degree of concentration and coordination

		(psychologists, oncologists, nurses) will give feedback through the Delphi process.		of experts' opinions.
Pilot RCT of Draft Intervention	To test the stage-matched psychological adaptation intervention for parent caregivers of children with leukemia in Pakistan.	A stage-matched intervention lasting 12 weeks with assessments conducted at baseline, mid-intervention, and end of intervention. 34 parent caregivers from each of the two study facilities (total N = 68).	A tertiary care hospital in Pakistan	Qualitative data will be transcribed and analysed. Two-tailed t-tests will be run for parametric quantitative data using 95% confidence intervals. Hedges' g formula, will be used to calculate effect sizes. Feasibility and acceptance will be measured by participants' ratings of the intervention's overall helpfulness. Baseline, midway, and post-intervention psychological adaptation and distress outcomes assessments will inform the program's initial efficacy.

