Participants: Parent caregivers (biological parents or step-parents of children diagnosed with leukemia. Participants who plan to relocate outside the study area during the study period will be excluded. The sample size estimation was initially derived using individual-level power calculations.

Sample size: The sample size was selected to (1) provide precise estimates of key feasibility parameters (e.g., recruitment rate, retention, adherence), (2) align with published pilot trial recommendations (Ying et al., 2025), and (3) reflect sample sizes used in comparable psychosocial intervention pilots in pediatric oncology settings (Koyu and Kilcarslan, 2024). We aim to recruit $N = 70$ parent caregivers (35 per arm). This sample size allows estimation of a 75% retention rate with a 95% confidence interval width of $\pm 13\%$. Accounting for an anticipated 25% attrition rate common in LMIC psychosocial trials, we will recruit up to 88 participants. This sample is sufficient to assess feasibility, acceptability, and preliminary effects, while informing sample size calculations for a future definitive RCT.

Setting: The study will be conducted in a tertiary care hospital in Pakistan providing pediatric oncology services.

Study procedures: The study will be conducted over 12 weeks, with interventions delivered by trained mental health professionals and outcome assessments carried out by research assistants. After recruitment, participants will provide informed consent and be screened for eligibility. Caregivers in the intervention group will receive a stage-matched psychological adaptation program based on the transactional family adaptation model and culturally adapted coping strategies. The final intervention protocol will be developed after the initial three stages.

Outcome evaluations will be conducted at baseline, mid-intervention, and post-intervention to assess feasibility, acceptability, adherence, and effectiveness, using methods such as diaries, observations, and satisfaction measures. At the end of the study, caregivers will participate in semi-structured interviews and complete questionnaires to evaluate outcomes. Additionally, professionals delivering the intervention will be interviewed to identify strengths of the trial and assessment methods. Key outcomes include improved psychological adaptation, reduced distress,

enhanced coping skills, and better quality of life among caregivers. Figure 4 summarizes the whole procedure for the pilot RCT.

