2.10.1 Method of Outcome and Process Evaluation

Preliminary psychosocial outcomes (psychological adaptation, distress, coping, and quality of life) will be assessed using validated tools such as the (1) sociodemographic information, (2) Psychological Adaptation Scale (PAS)(Biesecker et al., 2013), (3) Depression Anxiety and Stress Scale (DASS-21) (Lovibond&Lovibond, 1995), (4) Caregiver burden scale(Zarit et al., 1980)., (5) Perceived Social Support Questionnaire) l(Zimet et al., 1988).The Reach, Effectiveness, Adoption, Implementation and Maintenance (RE-AIM)(Glasgow et al., 1999) framework will be utilized for implementation outcomes.Process evaluation will examine feasibility outcomes (fidelity, acceptability, participant compliance, attendance, and assignment completion records, journal entries, qualitative interviews on perceived changes, and recruitment rate). The Client Satisfaction Questionnaire (CSQ-8) will be used for acceptability, with measures such as audio recordings, direct observation, and supervision logs as fidelity monitoring procedures.

Analyses: Detailed demographic and baseline characteristics will be provided, and all findings will be systematically analysed and documented. Quantitative analysis will cover recruitment and retention rates, participants' responses to the intervention, and session frequency and duration, as measured by the Client Satisfaction Questionnaire (CSQ). Qualitative interview data will be analysed using the same approach applied in the earlier stages of the program. The preliminary findings from the pilot RCT will decide whether we will advance to a comprehensive efficacy trial. This decision will be based on a comprehensive process evaluation of the intervention components, implementation, and trial procedures. Key considerations will include participant feedback on the acceptability, feasibility, and tolerability of the intervention, as well as the relevance and practicality of the outcome measures. These criteria and decision-making processes will be clearly specified in the pilot RCT protocol.

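### No count by arm is planned of caregivers whose DASS-21 worsens or who have an adverse psychological reaction: unintended outcomes are handled only qualitatively and distress scores only as efficacy

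*Protocol*

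**What the plan says.** Table 1 (section 2.3), in the row on outcome measures, lists "psychological distress such as depression, anxiety and Stress" among the outcomes and then says of anything unforeseen: "Unintended outcomes will be qualitatively explored through process evaluation". In the row on what professionals must do, the same table says: "A supervising psychologist will oversee sessions, address any adverse psychological reactions". It does not say that these reactions are logged or counted.

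For the pilot, section 2.10.1 names the DASS-21 as the distress instrument, and section 2.10 says: "Outcome evaluations will be conducted at baseline, mid-intervention, and post-intervention". Table 3 (section 2.4) plans two-tailed t-tests with 95% confidence intervals and Hedges' g, and gives the purpose of the scores: "Baseline, midway, and post-intervention psychological adaptation and distress outcomes assessments will inform the program's initial efficacy".

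The process evaluation in section 2.10.1 covers fidelity, acceptability, compliance, attendance, assignments, journals, interviews and recruitment. Fidelity is monitored by audio recording, observation and supervision logs. The same section makes tolerability, judged from participant feedback, one of the considerations for going on to an efficacy trial, and leaves the exact criteria to the pilot trial protocol.

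**The concern.** The protocol foresees adverse psychological reactions and intends to weigh tolerability, but plans no number that would show how many caregivers got worse in either arm.

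- The qualitative route leans on caregiver interviews at the end of the study (section 2.10). The protocol expects 25% attrition, which is 0.25 × 88 = 22 caregivers at the recruitment ceiling. It plans no interviews with those who withdraw.
- Control caregivers receive routine care only, so the supervised-session channel does not exist for them.
- Background distress is high. The Introduction cites, for similar contexts, "up to 87.8% of caregivers exhibit symptoms of anxiety, while 45.9% experience depression". Some worsening is plausible in any arm, and reports from the intervention arm alone cannot be set against it.

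At stake is the progression decision. The intervention could move to a large trial on a favourable mean, with no count of caregivers who deteriorated.

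**Working it through.** The protocol gives no figure on this point to reproduce. The check is a reading of the sections, followed by an illustration.

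**Step 1. What each planned source can show**

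| Source | Where | Both arms? | Counts caregivers who worsen? |
|---|---|---|---|
| Qualitative exploration of unintended outcomes | Table 1 | Not stated | No |
| Supervising psychologist in sessions | Table 1 | Intervention only | No; recording not mentioned |
| Audio recordings, supervision logs (fidelity) | 2.10.1 | Tied to delivery of the intervention | No |
| Diaries, observation, satisfaction measures | 2.10 | Not stated | No |
| DASS-21 mean scores | Table 3, 2.10, 2.10.1 | Implied | No; means only |

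That the DASS-21 is taken in both arms is implied by the two-arm design and by Table 1: "assessments at baseline, post-intervention, and follow-up will be conducted by research assistants blinded to group allocation". Blinding has a purpose only if both arms are assessed. That sentence lists a follow-up visit where section 2.10 lists a mid-intervention one. The two need reconciling, but both give three time points, so the point is unaffected.

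**Step 2. Can a mean improve while a minority worsens?**

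The inputs are assumptions, since the protocol gives no deterioration rate: a share p worsens by 1 SD and the rest improve by 0.4 SD. Mean improvement = (1 − p) × 0.4 − p × 1.0.

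- 4 of 44: (40/44) × 0.4 − (4/44) × 1.0 = 0.364 − 0.091 = 0.27 SD.
- p = 10%: 0.36 − 0.10 = 0.26 SD.
- p = 20%: 0.32 − 0.20 = 0.12 SD.

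In each case the mean shows benefit only. The 44 is half the ceiling of 88. Section 2.10 aims for 35 per arm, and Table 3 gives 34 per facility.

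**Step 3. What would a count deliver at this size?**

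Exact (Clopper-Pearson) 95% intervals; for zero events the upper limit is 1 − 0.025^(1/n). The chance of seeing at least one case at an assumed true rate of 5% is 1 − 0.95^n.

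| Caregivers per arm | 0 worsened | 4 worsened | Chance of at least one case at 5% |
|---|---|---|---|
| 35 | 0 to 10.0% | 3.2 to 26.7% | 83% |
| 44 | 0 to 8.0% | 2.5 to 21.7% | 90% |

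If 25% of 44 are lost, 33 remain. Zero events would then give 0 to 10.6%, and the chance of at least one case would be 82%.

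As a formal comparison the count is weak. Power for an assumed 10% against 30% is 55% with 35 per arm and 65% with 44, before any allowance for clustering. A count is useful as description and not as a test.

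**The case against.** A reader might infer that worsening distress is never compared between arms, or that such a comparison is impossible. The documents do not support that. Distress is a named outcome measured with the DASS-21 at three time points, and Table 3 plans two-tailed t-tests. Table 3 does not say outright that these are between arms, but that is the natural reading for a two-arm trial. A two-tailed comparison of means can show average harm. The gap is confined to individual deterioration and to adverse reactions.

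It would also be too strong to say that reactions can be noticed only in sessions. Diaries, journals, observation, supervision logs and interviews with the delivering professionals may all capture them, including for a caregiver who later leaves. That stands, but none of these is planned as a count, and the logs and recordings follow delivery of the intervention.

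The best counter-argument is deferral. Section 2.10 says that this stage is described briefly and leaves detail to a pilot trial protocol, and 2.10.1 leaves the progression criteria there too. A table of DASS-21 changes could also sit in an analysis plan. This lowers the weight of the point but does not remove it. Table 1 has already chosen a qualitative method, which the later document would inherit. DASS-21 worsening could be derived afterwards, but adverse reactions never asked about in the control arm cannot be recovered.

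Two further objections shape the remedy. The Limitations section confirms one intervention and one control facility, so any arm difference is confounded with facility, and a by-arm table cannot by itself separate harm from setting or natural course. And a shift in severity category cannot register worsening in caregivers already in the top category, while it would count a trivial change across a cut-off.

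Finally, the prevalences in the Introduction are for symptoms and say nothing about deterioration rates.

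**Conclusion.** The point holds in this limited form. The protocol handles unintended outcomes only qualitatively and uses distress scores only as an efficacy outcome. It plans no count by arm of caregivers whose DASS-21 worsens or who have an adverse psychological reaction, although tolerability feeds the progression decision.

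Its size cannot be derived from the protocol. The 0.27 SD improvement with 4 of 44 worsening rests on assumed values (about 10% worsening, 1 SD, 0.4 SD) and shows only that a mean can improve while a minority deteriorates. The conclusion also assumes that the DASS-21 is taken in both arms, which is implied but not stated.

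This is a worthwhile, inexpensive improvement to a stated method. It is not an error that invalidates the pilot.

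**What to change.** In Table 1 and section 2.10.1, and carried into the pilot trial protocol, keep the qualitative exploration and add the following:

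1. A descriptive table by arm of the number and proportion of caregivers, with exact 95% confidence intervals, whose DASS-21 subscale scores worsen from baseline to mid-intervention and from baseline to post-intervention. Define worsening in advance as an amount of score change, not only as a shift in severity category. Show withdrawals separately.
2. A record of adverse psychological reactions, obtained with the same question in both arms at the existing mid and post assessments, and tabulated by arm.
3. A statement that this table is used in the tolerability part of the progression decision.
4. A statement that, with one facility per arm, any arm difference is confounded with facility, so the table is descriptive and not a test.

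State explicitly that the DASS-21 is taken in both arms, and reconcile the assessment times in Table 1 with those in section 2.10.

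The cost is one extra table, drawn largely from data already planned, and one extra question at two existing assessments. No additional participants or visits are needed.

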2.5.2 Recruitment

The literature and professional contacts will inform the recruitment of expert participants. We will recruit parent caregivers of children with leukemia from pediatric oncology facilities in Pakistan (e.g., one in a major urban center like Peshawar and in a secondary city to capture diverse socioeconomic and cultural contexts).

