2.10 Stage 4: Pilot Trial of the Stage-Matched Intervention Draft

The last stage of the program involves testing the stage-matched psychological adaptation intervention with a population representing the participants expected to participate in a large-scale randomised controlled trial if the pilot trial produces positive productive result results. This stage is only described briefly; although the detailed procedure will be described in a protocol for the pilot trial.

Objective: The pilot trial aims to:

1. Evaluate the feasibility of the stage-matched psychological adaptation intervention among parent caregivers of children with leukemia and the acceptability of the intervention by participants.
2. Preliminarily investigate the efficacy of the intervention in improving psychological adaptation, coping, and reducing distress in parent caregivers.
3. Examine the acceptability of the stage-matched psychological adaptation intervention among parent caregivers of children with leukemia.

Method: This study will use a two-arm pilot randomized controlled trial design involving parent caregivers of children with leukemia in two facilities of a tertiary care hospital in Pakistan. To simplify implementation and minimize contamination, each facility will be randomly assigned to either the intervention or control group.

The intervention group will receive stage-matched psychological adaptation program alongside routine medical care, while the control group will continue with standard routine medical care. Cluster randomization at the facility level is employed to prevent potential spillover effects that could occur with individual randomization within the same setting. This approach reflects real-world practice, where interventions are typically implemented at the organizational level across entire facilities rather than targeting individual participants. Using cluster randomization also enhances intervention fidelity by allowing consistent delivery and standardized staff training within each facility. Moreover, it aligns the study design with practical implementation

conditions by accounting for variations in resources, workflows, and procedures across different facilities.

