Sustainability depends on the development of capacity. Hospital staff will be trained to deliver the intervention, a strategy shown to maintain fidelity even after the trial ends. Additionally, feasibility and acceptability data from the pilot will directly inform implementation planning for policymakers and administrators, focusing on the adoption and maintenance dimensions of RE-AIM.

Limitations

This pilot will be conducted within a single tertiary hospital, potentially limiting applicability to urban, well-resourced settings. Future research should involve multiple centers, including rural and underserved areas, where childhood cancer cases are diagnosed later and mental health resources are scarce. The study's reliance on self-reported measures may introduce social desirability bias, so integrating clinician-rated or observational assessments is recommended. The 12-week follow-up is insufficient for assessing long-term effects, so extended evaluations are needed. While culturally adaptable, further contextual adjustments may be required for specific subpopulations. Additionally, the pilot's small sample size limits statistical power; thus, a larger, multi-site trial is necessary to confirm efficacy. Lastly, excluding parents of children in the acute illness phase means findings may not reflect the highest-stress periods of the cancer journey. Additionally, the pilot RCT design with only two clusters (one intervention, one control facility) limits the statistical power for definitive hypothesis testing; therefore, the primary goal of this pilot study is to assess feasibility, acceptability, and preliminary efficacy, following CONSORT guidelines for pilot and feasibility trials (Eldridge et al., 2016). A fully powered multi-site randomized controlled trial would be required to establish definitive efficacy.

References

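### With one facility per arm, the intervention effect cannot be separated from the facility effect; the protocol presents this as a power limit and still plans t-tests and 95% CIs to inform efficacy

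*Protocol*

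**What the plan says.** Section 2.10 (Method) makes the facility the unit of randomisation: "each facility will be randomly assigned to either the intervention or control group". Limitations confirms that there is one facility in each arm.

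The last row of Table 3 gives the quantitative analysis: "Two-tailed t-tests will be run for parametric quantitative data using 95% confidence intervals", and "Hedges' g formula, will be used to calculate effect sizes". The same cell says that the repeated outcome assessments will inform initial efficacy. Objective 2 in section 2.10 is to "Preliminarily investigate the efficacy of the intervention in improving psychological adaptation, coping, and reducing distress in parent caregivers". The sample-size paragraph says that the number of caregivers was first derived from power calculations at the level of the individual, and concludes: "This sample is sufficient to assess feasibility, acceptability, and preliminary effects, while informing sample size calculations for a future definitive RCT". No ICC, design effect or cluster adjustment appears anywhere.

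The protocol comments on the consequences of the design in two places. Limitations says that "the pilot RCT design with only two clusters (one intervention, one control facility) limits the statistical power for definitive hypothesis testing". The Method text of 2.10 credits cluster randomisation with taking account of differences between facilities in resources and working practices.

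The two facilities are described in different ways. Section 2.5.2 gives as an example "one in a major urban center like Peshawar and in a secondary city to capture diverse socioeconomic and cultural contexts". Section 2.10 speaks of two facilities of one tertiary hospital, and Limitations says "This pilot will be conducted within a single tertiary hospital".

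**The concern.** When each arm is a single facility, any difference between arms is the intervention effect plus whatever already distinguishes the two facilities: case mix, staffing, family circumstances, standard of routine care. The data contain nothing that could divide the total into its parts. A t-test on caregivers treats them as independent and measures its error only by the spread within facilities. Its p-value and interval therefore leave out the facility component altogether.

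The protocol's diagnosis matters because it points to the wrong remedy. Low power is cured by more participants. Aliasing is not: more caregivers in the same two facilities estimate the same mixed quantity more precisely. The sentence in 2.10 about allowing for facility variation is wrong for this design, because one facility per arm cannot do that.

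At stake is the efficacy objective. A reader of the pilot report could take a significant t-test, or an interval that excludes zero, as a signal of efficacy when a facility difference alone would produce it. The feasibility and acceptability aims are not affected.

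**Working it through.** **Inputs from the protocol.** Two clusters, one per arm (2.10, Limitations). Two-tailed t-tests with 95% CIs, so nominal alpha is 0.05 (Table 3). Caregivers per facility, m: 34 (Table 3), 35 (2.10), or 44 if the full 88 are recruited (2.10). The protocol states no figure for the precision or error rate of the outcome comparison, so there is none to reproduce; its one precision figure concerns retention.

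**Assumed.** The ICC, the share of total variance that lies between facilities. The range shown is 0.01 to 0.10.

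**Step 1: degrees of freedom.** Clusters minus arms = 2 - 2 = 0. A t-test on facility means cannot be computed, and the ICC cannot be estimated apart from the intervention effect. A between-arm t-test is therefore only possible on individual caregivers.

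**Step 2: the variance that the t-test leaves out.** With total variance 1:
- true variance of the difference in means: 2 × [ICC + (1 - ICC)/m]
- variance that the t-test works with: 2 × (1 - ICC)/m
- ratio R = 1 + m × ICC/(1 - ICC)

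At m = 35 and ICC 0.05, R = 1 + 35 × 0.05/0.95 = 2.84, so the standard error is too small by a factor of √2.84 = 1.69.

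**Step 3: true type I error** = 2 × P(t with 2m - 2 df > critical value/√R). Simulation of 200,000 trials per setting agreed to within about 0.3 percentage points.

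| m per facility | ICC 0 | ICC 0.01 | ICC 0.02 | ICC 0.05 | ICC 0.10 |
|---|---|---|---|---|---|
| 34 | 5.0% | 9.0% | 13.0% | 23.6% | 36.4% |
| 35 | 5.0% | 9.1% | 13.2% | 24.1% | 37.0% |
| 44 | 5.0% | 10.2% | 15.3% | 27.8% | 41.5% |

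Coverage of the nominal 95% interval is 100% minus these figures: at m = 35, 90.9%, 86.8%, 75.9% and 63.0% for ICC 0.01 to 0.10. The error rises with m, so recruiting more caregivers makes the test worse.

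**Step 4: interval width, if the ICC were known to be 0.05, at m = 35.**
- needed half-width: 1.96 × √(2 × [0.05 + 0.95/35]) = 0.77 SD
- reported half-width: about 0.47 SD, from 1.96 × √(2/35); using only the within-facility variance, 1.96 × √(2 × 0.95/35) = 0.46 SD
- floor as m grows without limit: 1.96 × √(2 × 0.05) = 0.62 SD

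This illustrates scale only. The pilot cannot supply the ICC, so the 0.77 SD interval is not available as an alternative analysis.

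**Step 5: what g picks up with no intervention effect.** The facility difference alone has a standard deviation of √(2 × ICC/(1 - ICC)) within-facility SDs: 0.14, 0.20, 0.32 and 0.47 for ICC 0.01, 0.02, 0.05 and 0.10, whatever the number of caregivers.

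**The case against.** The strongest reply is that this is a pilot and its authors show restraint. Limitations mentions the two clusters, makes feasibility, acceptability and preliminary efficacy the goal, and calls for a fully powered multi-site trial before any definitive claim. Section 2.10 says that this stage is described only briefly and leaves detail to a separate pilot protocol. This stands as mitigation. It does not answer the point, because the confounding is never named, and no later plan could separate facility from intervention without assuming the ICC to be zero or known from elsewhere.

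Table 3 also does not say that the t-tests compare arms or treat caregivers as the unit; the next lines mention baseline, midway and post-intervention assessments, so tests of change within an arm are possible. The between-arm reading is an inference, though it is the only workable one for efficacy in a two-arm trial. Pre-post tests within an arm would not establish efficacy either.

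Three stronger readings are tempting and are not supported:
- That g will drive the decision to proceed. Section 2.10.1 bases that decision on process evaluation, participant feedback and the practicality of the measures, and names neither g nor a p-value. Nor does 2.10 say that g will size the definitive trial; informing sample size could mean SDs, recruitment and retention.
- That Hedges' g is itself invalid. It remains a legitimate description of the difference between two facilities. What fails is reading it as an intervention effect.
- That the sites are chosen to differ as much as possible. The two-city wording in 2.5.2 is an example about general recruitment of caregivers. It conflicts with the single-hospital description, but does not establish how different the pilot facilities will be.

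**Conclusion.** The point holds. One facility per arm leaves the intervention effect unidentified, and the between-arm t-tests and 95% CIs cannot be interpreted as evidence on it. This structural conclusion rests on the protocol's own description of the design and needs no assumed number. Limitations describes the problem only as limited power, and the statement in 2.10 that the design accounts for facility variation is incorrect.

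The size depends on assumed ICCs. At the stated 35 per arm, a nominal 5% test has a true error of about 9% at ICC 0.01 and 37% at ICC 0.10. It keeps 5% only if the ICC is zero, which two clusters cannot show. These figures assume equal cluster sizes, normally distributed outcomes and the between-arm, caregiver-level reading of Table 3.

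**What to change.** 1. **Table 3, pilot row:** remove between-arm p-values and efficacy CIs. Report means and mean changes for each facility, with within-facility CIs. Label any between-facility difference, including g, as descriptive and not separable from facility.
2. **Section 2.10, Sample size:** limit what the pilot informs to SDs, recruitment, retention and adherence. State that the definitive trial's ICC and target difference will come from outside this pilot.
3. **Limitations and 2.10, Method:** replace the power wording with a statement that the intervention effect cannot be separated from facility, and delete the claim that the design accounts for facility variation.
4. **Abstract, 2.2 (Stage 4), Table 3, 2.10 (Objective 2) and Limitations:** make the preliminary or initial efficacy wording consistent with descriptive outcomes only.
5. **Sections 2.5.2, 2.10 and Limitations:** reconcile the descriptions of the two facilities.

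The cost is wording. The pilot gives up an efficacy p-value that it could not validly produce; the design and N do not change. If the sponsor wishes to keep an efficacy objective, that would need more facilities per arm and a cluster-level or mixed-model analysis, which is a change of design.
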